### Missing / Incomplete AE Onset Dates:

For each missing / incomplete AE onset date, an interval (INT\_START, INT\_END) is defined. The true unknown analysis start date of the AE is assumed to be within this interval. If the AE onset date is completely missing INT\_START will be Min(AE end date, Date of informed consent) and INT\_END will be Min(AE end date, Date of last visit). If only the year of the AE onset date is non-missing INT\_START will be Min(AE end date, 01 JAN of the reported year) and INT\_END will be Min(AE end date, 31 DEC of the reported year). If only year and month of the AE onset date are non-missing INT\_START will be Min(AE end date, 01 of the reported month) and INT\_END will be Min(AE end date, Last date of the reported month). Completely missing AE end date will not be considered in this derivation step. Partially missing AE end date (i.e., year and month are non-missing or only year is non-missing) will be temporarily assigned the largest possible date in the observed year or month and year in this derivation step. After this the imputed AE onset dates will be derived based on the intervals (INT\_START, INT\_END). If the date of first drug administration is within the interval [INT\_START, INT\_END] then the imputed AE onset date will be the date of drug administration. If the date of first drug administration is before INT\_START then the imputed AE onset date will equal INT\_START. If the date of first drug administration is after INT\_END or missing then the imputed AE onset date equals INT\_END.

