9.2.1 Selection of study population

Site selection:

Sites in countries with launch dates prior to 1st Jan 2015 and known to prescribe Gi(l)otrif[®] on a regular basis will be chosen. Asian and Non-Asian countries will be included.

Inclusion criteria:

All consecutive patients will be included if all the following criteria are present:

- Age \geq 18 years

Protocol for non-interventional studies based on existing data

BI Study Number 1200.270

c09038525-01

Proprietary confidential information © 2016 Boehringer Ingelheim International GmbH or one or more of its affiliated companies

- Patients with EGFR mutation (common mutations), TKI-naïve advanced NSCLC, treated with Gi(l)otrif[®] as the first-line treatment for NSCLC within the approved label
- Signed and dated written informed consent per regulations. (Exemption of a written informed consent for retrospective observational studies in some countries per local regulations and legal requirements.)

Exclusion criteria:

Patient won't be included if any of the following criteria is present:

- Any contraindication to Gi(l)otrif[®] as specified in label.
- Patients with uncommon mutations are excluded as uncommon mutations are not within label in all participating countries (e.g. USA).
- Patients still on treatment with Gi(l)otrif[®] will be excluded unless treatment period is ≥ 6 months.
- Patients treated with Gi(l)otrif[®] within an interventional trial.

A log of all patients included into the study will be maintained in the ISF at the investigational site.

Patients treated with Gi(l)otrif[®] in interventional trials are excluded to ensure the non-interventional setting of this study. The threshold of ≥ 6 months treatment with Gi(l)otrif[®] for patients being still on treatment was chosen to avoid early censoring and enable collection of mature data on ADRs and treatment duration. However, patients who stopped Gi(l)otrif[®] < 6 months will be included to avoid bias. All patients fulfilling inclusion and exclusion criteria from a site will be entered to avoid bias. The maximum of 15 patients per site was chosen to avoid bias by high proportion of patients coming from one site.

BI reserves the right to discontinue the study overall or at a particular study site at any time for the following reasons:

1. Failure to meet expected enrolment goals overall or at a particular study site.

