9.3 VARIABLES

Data will be documented from the date of first dose of Gi(l)otrif[®] treatment until the date of last dose of Gi(l)otrif[®] treatment or end of data collection whichever occurs first.

During the data collection period, the following data will be collected from medical records in an eCRF by investigators during the study:

- Informed consent
- Diagnosis
- Demographics (gender, date of birth, ethnicity)
- Body weight and height at start of Gi(l)otrif[®] treatment
- ECOG performance score at start of Gi(l)otrif[®] treatment
- EGFR mutational subgroup (Del19/L858R)
- Starting dose of Gi(l)otrif[®]
- Start date of Gi(l)otrif[®] treatment
- End date of Gi(l)otrif[®] treatment
- Gi(l)otrif[®] dose modification(s) and date(s)
- ADRs
- Concomitant medications (limited to medication for management of diarrhea, skin effects, mucositis/stomatitis as dichotomous variables (e.g. received anti-diarrhea medication yes/no))
- Reason for dose modification(s)
- Date of progression
- Type of progression:
 - a. clinical
 - b. radiographic
 - c. both clinical/radiographic progression

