10.1.1 Study approval, patient information, and informed consent

This study will be initiated only after all required legal documentation has been reviewed and approved by the respective IRB / IEC and competent authority (CA) according to national and international regulations. The same applies for the implementation of changes introduced by amendments.

In some countries, retrospective observational studies can be exempt from a written informed consent per local regulations and legal requirements, IRB / IEC often grants a waiver of consent for retrospective chart review studies. In order to avoid bias by exclusion of subjects that cannot be given informed consent for any reason like death, missing contact information etc., exempt from a written informed consent should be asked for such situations.

In case such a waiver is not given, prior to patient participation in the study, written informed consent must be obtained from each patient (or the patient's legally accepted representative) according to ICH GCP and to the regulatory and legal requirements of the participating country.

Each signature must be personally dated by each signatory and the informed consent and any additional patient-information form retained by the investigator as part of the trial records. A signed copy of the informed consent and any additional patient information must be given to each patient or the patient's legally accepted representative.

The patient must be informed that his / her medical records may be examined by authorised monitors (CML / CRA) or Clinical Quality Assurance auditors appointed by Boehringer Ingelheim, by appropriate IRB / IEC members, and by inspectors from regulatory authorities.

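### For completely missing AE onset dates the SAP anchors on the consent date, so an ADR still present at a dose reduction that precedes consent is never dated before that reduction

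*SAP*

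**What the plan says.** The SAP section on missing or incomplete AE onset dates builds an interval, presumes that it contains the real onset, and then picks a date. For a completely missing onset:

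- INT_START "will be Min(AE end date, Date of informed consent"; INT_END is the earlier of the AE end date and the last visit.
- If first dose lies inside the interval, the onset becomes the first-dose date. If first dose is earlier than INT_START, "then the imputed AE onset date will equal" INT_START. Otherwise it becomes INT_END.
- A completely missing end date is ignored. A partial end date "will be temporarily assigned the largest possible date in the observed year or month and year in this derivation step".

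The branches for year-only and year-and-month onsets do not use the consent date.

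In the protocol, data are documented from first dose until last dose of "treatment or end of data collection whichever occurs first" (section 9.3). On consent, section 10.1.1 states: "This study will be initiated only after all required legal documentation has been reviewed and approved by the respective IRB / IEC". Where no waiver is given, "prior to patient participation in the study, written informed consent must be obtained from each patient". The same section notes that an "IRB / IEC often grants a waiver of consent for retrospective chart review studies". The title page is dated 1 March 2016. Section 9.7.1 compares common ADRs before and after a dose modification made in the first 6 months of treatment, and in the same paragraph says that missing ADR dates will be imputed.

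**The concern.** A consent-date anchor suits a study in which consent comes before the first dose, because the interval then covers all treatment. Here the order is usually reversed: treatment, and often the reduction, lie in the past when the patient consents. For an ongoing ADR the interval then leaves out all treatment before consent, which conflicts with the SAP's premise that the interval contains the real onset.

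The pre/post comparison serves the primary objective. An ADR present at a reduction may be the reason for it, yet if imputed onset decides the period, the rule takes that ADR out of the pre count. Section 9.9 expects gaps in the records, so some missing dates are foreseeable.

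**Working it through.** **Notation.** F = first dose, R = reduction within 6 months of F, C = consent, E = AE end date, L = last visit.

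**1. When does consent follow the reduction?** C is on or after 1 March 2016 (title page date; section 10.1.1). Six months back is 1 September 2015: a start on 31 August 2015 reaches its 6-month point on 29 February 2016. So R < C for every consented patient with F before 1 September 2015. Counting from the planned start of data collection (31 May 2016) would move the bound to 30 November 2015, so the earlier date is cautious.

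For later starters it depends on timing. Patients still on treatment "will be excluded unless treatment period is ≥ 6 months" (section 9.2.1). If that threshold, or the end of treatment, has been reached by consent, then R < C. No text ties the two. If consent is on day 30 and the reduction on day 60, the rule gives day 30, which is before the reduction, so no problem arises.

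**2. The rule with F < R < C and an ADR still present at R (E on or after R, or no E).**

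- No E: INT_START = C, so onset = C, after R.
- E before C: INT_START = E, so onset = E, on or after R.
- E on or after C: INT_START = C, so onset = C, after R.

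In a check on 400,000 random date sets (F from 12 July 2013 to 31 August 2015, C from 1 March to 31 December 2016; assumed ranges), 0 onsets fell before R, 167 on R and 399,833 after R. ADRs with a complete end date before R all stayed before it (397,819 of 397,819). With F as anchor, all 400,000 fell before R.

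**3. Example (dates assumed).** F 1 Feb 2015, R 15 Mar 2015, last dose 1 Dec 2015, L 15 Dec 2015, C 15 Jul 2016; onset completely missing.

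| Recorded end | Imputed onset | Result |
|---|---|---|
| 5 Mar 2015 | 5 Mar 2015 | pre |
| Feb 2015 | 28 Feb 2015 | pre |
| 20 Mar 2015 | 20 Mar 2015 | post |
| Mar 2015 | 31 Mar 2015 | post, even if it ended before 15 Mar |
| 2015 | 31 Dec 2015 | after last dose; interval reversed |
| none | 15 Jul 2016 | after last dose; interval reversed |

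The interval is reversed in the last two rows because INT_END is the last visit, 15 Dec 2015, which precedes INT_START. If the same patient were still on treatment with a last visit on 1 Aug 2016, the last row would give 15 Jul 2016, inside treatment and not reversed. If consent were waived and there were no end date, INT_START would be undefined.

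The branches also disagree. In this patient with no end date, an onset recorded only as 2015 has the interval 1 Jan to 31 Dec 2015, which contains F, so it is imputed to 1 Feb 2015. A completely missing onset goes to 15 Jul 2016.

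**4. Size.** The documents give no figure to reproduce. Assumed truth: LUX-Lung 3 diarrhoea rates in dose-reduced patients (protocol section 7), p = 99.2% before and q = 46.7% after, so p − q = 52.5 points; for grade ≥3, 20.5% and 4.1%, so 16.4 points. Let m be the assumed share of pre- or post-reduction patients actually misdated.

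| Scenario under the SAP rule | Formula | m = 2% | 5% | 10% |
|---|---|---|---|---|
| A. Pre ADRs redated into post (counted by onset, post window open) | p(1−m) − [q + (1−q)pm] | 49.5 | 44.9 | 37.3 |
| B. Pre falls, post unchanged | p(1−m) − q | 50.5 | 47.5 | 42.6 |
| C. Same ADRs lost from both periods | p(1−m) − (q − pm) | 52.5 | 52.5 | 52.5 |
| D. Both counts lose share m | (1−m)(p − q) | 51.5 | 49.9 | 47.3 |
| E. Post ADRs dated after last dose and lost, pre intact | p − q(1−m) | 53.4 | 54.8 | 57.2 |

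At 10%, A is 89.28 − (46.7 + 0.533 × 9.92) = 89.28 − 51.99 = 37.3, an error of −15.2. E is 99.2 − 42.03 = 57.2, an error of +4.7. A assumes that moved patients are independent of those already counted in post; C assumes that each lost ADR was present in both periods. For grade ≥3 at 10%, A to E give 12.4, 14.4, 16.4, 14.8 and 16.8.

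**5. The first-dose anchor on the same footing.** If share m of post-reduction patients is moved to pre, the fall is p + (1−p)qm − q(1−m) = 53.4 / 54.9 / 57.2 (grade ≥3 at 10%: 17.1).

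**The case against.** Several points on the other side have force.

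- *Collection window.* Protocol section 11.2 has ADRs entered in the eCRF from consent onwards. Read literally, no earlier ADR would be recorded and a consent anchor would be coherent. The point therefore takes section 9.3 (data from first dose) as governing. That is the natural reading, because a pre/post analysis of early reductions would otherwise have no pre period where consent follows the reduction. The dependency is real, and the two sections need reconciling.
- *Frequency.* The eCRF has automatic completeness checks (section 9.8), and about 30% of patients undergo source data verification (sections 9.4 and 9.8). Completely blank onsets may be few. This stands.
- *Unseen text.* The planned tables that the SAP announces, and the internal SOPs that section 9.7.1 cites for imputation, are not in the text available here. They may settle whether a persisting ADR is counted by onset or by presence, and when the post period ends. This limits what can be said about the effect, not about the dates the rule yields.
- *The remedy is a convention too.* The first-dose anchor leans towards pre and favours a larger fall, the direction that section 7 suggests. This stands, and is why sensitivity analyses are needed. It does not rescue a rule that can place an onset after the last dose or the last visit, and that disagrees with the SAP's own year-only branch.
- *The analysis is descriptive.* True, and it limits the weight of the point, but the comparison serves the primary objective.

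**Conclusion.** The rule is wrong as written for this design. For completely missing onsets, an ADR still present at an early reduction is never dated before it when consent follows the reduction. That condition is certain for consented patients starting before 1 September 2015 and depends on timing for later starters. For stopped patients the imputed onset can also fall after last dose and last visit, and INT_START is undefined when consent is waived and there is no end date.

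The size is unknown and the sign is not determined. With 10% of pre- or post-reduction patients assumed misdated and LUX-Lung 3 rates assumed true, the scenarios for the 52.5-point all-grade fall run from about 37.3 to 57.2. They are illustrations, not bounds.

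A reader might infer more than the documents support:

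- *That the rule always understates the fall.* It does not: true post-reduction ADRs in stopped patients can be dated at consent and lost from post, which overstates the fall.
- *That m is the share of missing onsets.* A patient leaves the pre count only if the onset is fully missing, the ADR is still present at the reduction or has a partial end date that is moved past it, and no other episode of that ADR is dated before it. So m may be well below that share.
- *That all incomplete dates are affected.* Partial onsets do not use the consent date, and ADRs with a complete end date before the reduction stay pre.
- *That the overall percentage with ADRs by severity is distorted.* That follows only if it is limited to an on-treatment window.

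The point is worth correcting before analysis, mainly because the error in the rule is plain and its repair nearly free.

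**What to change.** 1. In the SAP, in INT_START for completely missing onsets, replace the consent date with the first-administration date that the SAP already uses for time on treatment. This also resolves the undefined case under a waiver, and it matches the year-only branch when first dose falls in the recorded year.
2. Report how many onsets were imputed this way.
3. Repeat the pre/post comparison (i) excluding completely missing onsets and (ii) assigning to post those not known to have ended before the reduction. An ADR stays pre in (ii) if its complete end date, or the latest day allowed by a partial end date, precedes the reduction.
4. If the table specifications do not already say so, state whether a persisting ADR is counted by onset or by presence, and when the post period ends.
5. Reconcile protocol sections 9.3 and 11.2 on the ADR collection window.

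Items 1 to 4 cost one line in the derivation, one count, two reruns of a planned comparison and at most one sentence; item 5 is a wording clarification. No new data fields are needed.

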9.7 DATA ANALYSIS

9.7.1 Main analysis

All collected data will be analysed separately for patients starting with 40mg and \leq 30mg. Although due to anticipated low sample size in patients starting with \leq 30mg, it will be mainly for exploratory purpose. Baseline demographics will be analysed with descriptive statistics (N, median, mean, 25%, 75% percentile, SD) and compared descriptively between patients who have dose modifications within the first 6 months of Gi(l)otrif[®] treatment and those who do not. All the demographics, safety and efficacy data from this study in real-world setting will be compared with data from LUX-Lung 3 trial in descriptive manner.

Analysis of Safety:

[figure not shown]
Safety analysis will include all patients treated with Gi(l)otrif[®] and be descriptive in nature. Incidence and severity of ADRs according to Common Terminology Criteria for Adverse Events (CTCAE) criteria (version 4.0) ([R15-5988](#)) when available will be summarized and displayed in number/percentage. For patients who had Gi(l)otrif[®] dose modifications within the first 6 months of Gi(l)otrif[®] treatment, frequency and severity of the common ADRs pre- and post-dose modification will be analysed (\geq 40mg vs $<$ 40mg; and \geq 30mg vs $<$ 30mg). Missing or incomplete ADR dates will be imputed according to BI internal SOPs.

Analysis of Effectiveness:

Effectiveness analysis will include all patients treated with Gi(l)otrif[®]. Time on treatment is from the date of first dose of Gi(l)otrif[®] treatment to the date of last dose of Gi(l)otrif[®] treatment. Time to progression is from the date of first dose of Gi(l)otrif[®] treatment to the earliest date of documented progression (clinical, radiographic or both clinical/radiographic progression) or death. Time on treatment and time to progression will be estimated using Kaplan-Meier method, and the median along with two-sided 95% CI will be displayed (use the Greenwood's formula for estimation of standard errors). Log-rank test will be applied to compare between patients with and without dose modifications. Time on treatment and time to progression will be compared between patients who dose reduced to $<$ 40 mg within the first 6 months of Gi(l)otrif[®] treatment and those who remained on Gi(l)otrif[®] 40 mg once daily. This is in analogy to the analysis made on LUX-Lung 3 where a cut-off of 6 months was used as most dose reductions occur during this time.

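### Onset-date imputation ignores the dose-modification date: ambiguous partial dates count as pre, completely missing ones mostly as post, and no sensitivity analysis is shown

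*SAP*

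**What the plan says.** Protocol 9.7.1 (Main analysis, safety) states that, for patients modified within the first 6 months, "frequency and severity of the common ADRs pre- and post-dose modification will be analysed", contrasting ≥40 mg with <40 mg and ≥30 mg with <30 mg. For incomplete ADR dates it refers only to the sponsor's internal SOPs, so the SAP section on missing or incomplete AE onset dates is the only rule set out.

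That section first builds an interval of possible dates:

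- "If only year and month of the AE onset date are non-missing": the reported month, capped at the event end date.
- "If only the year of the AE onset date is non-missing": the reported calendar year, capped in the same way.
- "If the AE onset date is completely missing": from the earlier of event end and informed consent to the earlier of event end and last visit.
- "Completely missing AE end date will not be considered in this derivation step", so a missing end date drops out of these minima.

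It then picks one date:

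- First dose inside the interval: "then the imputed AE onset date will be the date of drug administration".
- "If the date of first drug administration is before" the interval: the interval start.
- First dose after the interval, "or missing then the imputed AE onset date equals" the interval end.

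The modification date, which Protocol 9.3 lists as collected, plays no part.

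**The concern.** A rule anchored on first dose suits the question of whether an event is treatment-emergent. The pre/post table asks a different question: did the reaction start before or after the dose changed? An uncertain onset is settled there by a rule that knows nothing about the change.

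The percentage of patients with ADRs by severity is a primary outcome (Protocol 9.3.2.1), and the effect of dose modification on ADRs is in the primary objective (section 8). The study takes its rationale from a LUX-Lung 3 post-hoc analysis in which reactions fell after reduction, so a shift between periods created by imputation bears directly on the main safety message. Data come from existing charts, and Protocol 9.9 treats anything not in the file as missing, so incomplete onset dates are plausible.

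**Working it through.** The plan states no figure to reproduce. The check applies the SAP rule literally, first to one case and then to simulated ADRs. ADRs are assigned to pre or post by onset date; that is an assumption.

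**Formula.** For a partial date with first dose known and not after the interval, the first two branches reduce to: imputed onset = max(interval start, first dose), the earliest on-treatment date possible. If the modification lies after that date but within the interval, the ADR is classed as pre whatever the truth. For a completely missing onset with consent after first dose (the usual order in a chart study) and first dose before event end, the second branch gives: imputed onset = min(event end, consent).

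**Worked case (invented dates).** First dose 10 Jan 2015, modification 20 Mar 2015, true onset 28 Mar 2015 (post), consent 1 Jul 2016.

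| Recorded onset | Imputed onset | Class |
|---|---|---|
| Mar 2015 | 1 Mar 2015 | pre (wrong) |
| 2015 | 10 Jan 2015 | pre (wrong) |
| none, end date 20 Apr 2015 | 20 Apr 2015 | post |
| none, no end date | 1 Jul 2016 | post |
| Mar 2015, first dose missing | 31 Mar 2015 | post |

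A month-only date after the modification month is unaffected: April 2015 becomes 1 Apr 2015, correctly post.

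**Partial dates, simulated.** Assumptions, none from the documents: first dose uniform over a calendar year; modification time exponential with mean 60 days, restricted to 7-182 days; true onset drawn independently of the modification, either exponential with mean 75 days or uniform over 330 days; no event end date.

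| Quantity | Month-only | Year-only |
|---|---|---|
| True post ADRs moved to pre, early-clustered onset | 17% | 79% |
| True post ADRs moved to pre, uniform onset | 5% | 61% |
| Straddling dates truly post, early-clustered onset | 47% | 51% |
| Straddling dates truly post, uniform onset | 52% | 77% |
| Straddling dates imputed as post | 0% | 0% |
| ADRs moved from pre to post | 0% | 0% |

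**Completely missing onsets, simulated.** A second set of assumptions: first dose uniform over 2014-2015, modification uniform on days 14-183, onset uniform on days 0-365, event duration 3-59 days, consent uniform from 31 May to 31 Dec 2016 (the data-collection window in Protocol section 6). The true pre share is about 27%. With an end date, the imputed pre share is about 19%, so about 8% of ADRs move from pre to post (27 − 19 = 8). Without an end date, the imputed pre share is about 0%, so about 27% move.

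**Direction.** For a reduction, partial dates inflate the higher-dose period and so favour reduction, while completely missing dates inflate the lower-dose period and work against it. For an escalation, pre is the lower dose and both effects reverse. Protocol 9.5 expects around half of the roughly 50 patients with a modified starting dose to be further de-escalated or escalated, so escalations are foreseen.

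**Related gap.** Protocol 10.1.1 allows consent to be waived. There is then no consent date, and the interval start for a completely missing onset is undefined if the end date is missing too.

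**The case against.** A reader might infer that the rule always takes the earliest possible date, only ever moves reactions from post to pre, and so manufactures a benefit of dose reduction. The documents do not support this. The third branch gives the latest date when first dose is missing or after the interval, completely missing onsets land late, and escalations reverse the sign. The direction stands for partial dates at reductions, not for the comparison as a whole.

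The simulations draw onset independently of the modification, whereas Protocol section 7 describes adjustment as guided by tolerability. A reaction that prompted the change did start before it, and pre is then correct. If half of straddling month-only ADRs were triggers (an assumption), the truly-post share would fall from 47-52% to about 24-26% (0.5 × 47% to 0.5 × 52%). This lowers the error without removing it. Uniform onset also sits poorly with LUX-Lung 3 as cited in section 7, where diarrhea was 99.2% before reduction and 46.7% after; that is a reason to quote ranges.

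Assignment by onset is inferred. Protocol 9.7.1 does not say how ADRs are allocated, or how one ongoing across the change is counted, and the available SAP text does not show the planned tables. The analysis is also descriptive, and incomplete dates may be rare. These points limit the size of the concern. They do not supply a rule suited to the pre/post question.

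**Conclusion.** The concern holds in this form: the imputation rule is built for treatment-emergence and, applied to the pre/post comparison, settles ambiguous ADRs without using the modification date. With assignment by onset, every straddling partial date goes to pre (first dose known and not after the interval) and most completely missing onsets go to post. Opposing errors need not cancel, so the table would partly measure date completeness.

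The percentages in the working apply per incomplete date and rest on assumed onset patterns. They are modest for month-only dates and large for year-only dates. The effect on the overall result and its net direction cannot be stated, because the share and mix of incomplete dates are not given. No sensitivity analysis for imputed dates appears in either document. The rule should be changed for this analysis before the tables are run.

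**What to change.** Keep the present rule for deciding treatment-emergence. For the pre/post tables, add to the SAP:

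1. State that ADRs are assigned by onset date, and how one ongoing across a modification is counted.
2. Define the possible on-treatment onset interval. For partial dates it is the SAP interval, starting no earlier than first dose. For completely missing onsets it runs from first dose to the earlier of event end and last visit, which also removes the dependence on a consent date.
3. When that interval contains the modification date, do not impute. Show the ADR in a row for pre/post not determinable.
4. Report the pre/post percentages twice, with these ADRs all pre and all post, separately for reductions and escalations.

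This uses only variables listed in Protocol 9.3 and dates the SAP rule already relies on. Using the dose at ADR onset instead would need an item that 9.3 does not list.

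The cost is one SAP paragraph, one extra row and a bounding table, with somewhat less precise pre/post percentages. If incomplete dates are rare, the bounds will nearly coincide and show that the issue is minor.
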